Wang and colleagues arbitrarily chose to deliver five sessions of rTMS. However, there are no empirical data on the duration of rTMS required to induce meaningful synaptic changes. Therefore, we will focus on the number of sessions as our rTMS parameter of interest while using the same stimulation parameters (e.g. frequency, intensity, duration) as Wang et al. (2014). We are choosing to focus on optimizing the number of sessions, rather than the other delivery parameters, because only one parameter can be explored at a time and reducing the number of sessions will have the greatest effect on the feasibility of this and future studies.

To find the minimum number of rTMS sessions required to produce a change in FC equivalent to that found by Wang et al., we will employ the continual reassessment method (CRM), a Bayesian, adaptive design, used to determine the dosing in Phase I drug trials. It is felt to be more efficient and accurate than simple dose escalation studies at estimating target drug doses (Garrett-Mayer, 2006). The parameter usually determined by this method is the minimum dosage expected to produce toxicity, or maximum tolerated dose (MTD). In this case, the MTD corresponds to the minimum number of sessions expected to produce the criterion change in FC. The logistical

function relating dose and effect and the MTD—the level where some predetermined proportion of subjects’ experience “toxicity”—is initially assumed from prior knowledge and then adjusted dynamically, based on response data from small cohorts of subjects dosed at successively higher or lower levels as the MTD is approximated. Cohorts are run iteratively until either a pre-specified number of participants is run, or another stopping rule has been reached (see statistical analysis section).

d. Examining the effect of rTMS stimulation on implicit and explicit memory systems

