Eligibility Checklist: See Appendix B.

4. Study Design and Methods

a. Study overview

This study will include 2 experiments, each using rTMS and MRI. Experiment 1 will use parietal rTMS. Experiment 2 will involve parietal and vertex rTMS. Experiments 2 will have the same learning and memory testing.

Experiment 1 will require a maximum of 8 visits (contingent on the results of Experiment 1) and a maximum time commitment of about 13 hours.

Experiment 2 will require a maximum of 8 visits (contingent on the results of Experiment 1) and a maximum time commitment of about 15 hours.

b. Recruitment

Healthy participants will be recruited from the pool of individuals self-referring to the study directly and via the NIH Clinical Research Volunteer Program. Although NIH employees will be allowed to participate, no direct solicitation of employees/staff by supervisors or co-workers will take place. All recruitment material will be IRB approved. Participants who indicate interest will be pre-screened over the phone. Pre-screening questions will include the following questions (Appendix A):

Are you between 18 and 50 years of age?

Are you in good health?

Are you taking any medications?

Are you prone to seizures, stroke, or migraines?

Are you free of a history of significant neurological or psychiatric conditions?

Are you free of any metal in your body?

Are you comfortable doing a one-hour MRI?

Are you able to visit the lab for up to 8 visits in a two-week period, and up to 7 visits in a week?

Participants will not be invited to participate in more than one Experiment for this protocol. Thus, participants in Experiment 1 will not be invited to participate in Experiment 2.

It is likely that some participants will miss some sessions. If this occurs, and the participant is still willing to participate, we will reschedule. If the subject has already received rTMS, we will wait at least 30 days to reschedule the session so that the effects of stimulation wash out. If a participant misses a session after baseline measures have been collected, baseline measurements will be performed again (e.g. MRI, behavioral assessments).

The study is requesting a waiver of consent documentation to conduct phone pre-screening on potential subjects prior signing main research consent to verify eligibility.

c. Screening

Participants who pass initial screening will be invited to participate in the study and scheduled for consent and formal screening.

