We will use the continual reassessment method (CRM) design (O’Quigley et al., 1990) to find the optimal number of sessions to produce a clinically meaningful change in fMRI connectivity between the parietal cortex and hippocampus in healthy subjects. The CRM is an adaptive design for dose finding studies, in which a “dose-toxicity” curve is fitted to the data and each patient will be assigned the dose most likely to be associated with the target toxicity level, designated as maximum tolerated dose (MTD) (Garrett-Mayer, 2006). It is important to note that while we retain the toxicity terminology from the CRM literature in the following description, we have adapted the technique to finding the threshold for efficacy, not toxicity.

In our study, the escalation decisions will be based on the efficacy of the rTMS. For the purpose of this study, the term dose will be used to mean the number of rTMS sessions. Similarly, the term toxicity will correspond to efficacy of the rTMS.

First, we used the data by Wang et al. (2014) to determine the threshold value for a clinically meaningful change in connectivity. The optimal cut-point for dichotomizing FC change was 0.028, which was determined by maximizing the Youden’s index (sensitivity+specificity1) in the ROC analysis.

The details and assumptions to implement CRM are as follows.

- **Dose limiting toxicity (DLT):** We assume that a FC change equal to or greater than the threshold value 0.028 is an effective change. DLT will be defined as the FC change from baseline to post-stimulation ≥ 0.028
- **Target toxicity level (TTL):** The sensitivity for the dichotomized FC change (at 0.028) in the parietal stimulation group was 87.50% in Wang et al. (2014). TTL is set to 12.5%, which is equal to (1-sensitivity). *The MTD is then defined as the number of rTMS sessions that has a risk of DLT equal to the chosen TTL value of 12.5%.*
- **Dose levels:** The dose level refers to the number of consecutive rTMS sessions.

The range of sessions is 1 to 5.

- **Number of healthy volunteers per dose level:** 3 healthy volunteers per dose level
- **Dose-toxicity model:** We propose to use a one-parameter hyperbolic-tangent dose-response model by O'Quigley et al. (1990), where a Gamma (1, 1) prior will be used.
- **Starting dose:** 3 sessions
- **Stopping rule:** Healthy volunteers will continue to be recruited to the trial until a fixed sample size of 15 is achieved.

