We based our sample size estimate on the behavioral results from the study we are replicating (Wang et al., 2014). In Wang et al. (2014), the effect size of the memory increases caused by PPC stimulation, compared to sham stimulation, was 0.75 (Cohen's d). This was achieved using a within-subjects design. Using this effect size, to achieve a β of 0.70 using the between subjects design described in this protocol (Experiment 2), 16 participants are required.

Sixteen subjects per group also achieves sufficient power to detect FC changes. Wang et al. indicate that the mean difference in FC from post to pre stimulation in retrosplenial region was 0.1018 and its standard deviation was 0.09296. Based on their data, we assume that the mean change will be between 0.1008 and 0.1028. We also assumed its standard deviation (SD) will be between 0.085 and 0.10. A one-tailed, paired t-test was used at a significance level of 0.05. Computations were carried out using PASS (Hinze J. [2008] PASS, NCSS, LLC, Kaysville, Utah).

The following table shows estimates of power to address Primary Aim 1 given ten subjects per treatment group.

Mean of paired difference	Estimated standard deviation of the difference	Power
0.1008	0.085	0.96440
0.1018	0.085	0.96698
0.1028	0.085	0.96940
0.1008	0.093	0.93446
0.1018	0.093	0.93833

0.1028	0.093	0.94202
0.1008	0.100	0.90159
0.1018	0.100	0.90651
0.1028	0.100	0.91125

Table 1. Estimated power for primary aim 1 (N=10 in parietal group)

A sample size of ten subjects per group achieves 93.8% power to detect a mean of paired differences of 0.1018 with an estimated standard deviation of differences of 0.093 and with a significance level of 5% using a one-sided paired t-test. Under other scenarios, the estimated powers were greater than 90%.

Assuming a 50% dropout rate, we anticipate enrolling up to 101 healthy subjects (33 for Experiment 1; 64 for Experiment 2).

11. Human Subjects Protection

a. Subject selection

We will recruit healthy participants through referrals from the NIH Clinical Research Volunteer program or through self-referrals to the protocol. We will work to ensure equitable selection.

b. Justification for exclusion of subjects

i. Justification for exclusion of children

Children will not be included. The study is predicated on the work of Wang et al. (2014) who studied participants over the age of 18. Therefore, in order to replicate this result, we will recruit a sample of the same age.

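### Experiment 1 has no reference for how often FC rises by 0.028 without effective stimulation, so its session number cannot be reported as the number required

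*Combined protocol and SAP*

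**What the plan says.** Section 4.a states "Experiment 1 will use parietal rTMS". Under Experiment 1 in section 4.d, subjects differ only in the number of stimulation days, and section 10.a.i sets the levels at 1 to 5 sessions with no zero level. Section 4.d.iii assigns the vertex control to the later experiments.

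Section 10.a.i defines success for one subject: "DLT will be defined as the FC change from baseline to post-stimulation ≥ 0.028". On the origin of the threshold it says "The optimal cut-point for dichotomizing FC change was 0.028, which was determined by maximizing the Youden’s index", using the source study's data. It then reports "The sensitivity for the dichotomized FC change (at 0.028) in the parietal stimulation group was 87.50" percent, and continues "TTL is set to 12.5%, which is equal to (1-sensitivity"). The specificity is not given.

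Specific Aim 1 asks how many sessions are required for a substantial change in FC. The background in section 1.c is worded more strongly, as "the minimum number of rTMS sessions required to produce a change in FC equivalent to that found by" the source study. Sections 4.d.viii and 10.a carry the selected number into Experiment 2.

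The only spread of FC change in the documents is in section 10.b: "the mean difference in FC from post to pre stimulation in retrosplenial region was 0.1018 and its standard deviation was 0.09296". The power table there assumes an SD of 0.085 to 0.10.

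**The concern.** Saying that a number of sessions is required to produce a change is a causal statement. It needs to be known how often the same change appears when stimulation has no effect. Experiment 1 contains nothing that estimates this, because every subject is stimulated at the target site and each is compared only with his or her own baseline scan.

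Maximising Youden's index uses both sensitivity and specificity, so a specificity at 0.028 must have been available. It is the figure that would indicate the background rate, and it is the one left out. Section 1.b argues that FC is stable, but from identification of individuals and general reliability. It gives no within-subject SD for the parieto-hippocampal pair, so it cannot show that 0.028 lies outside scan-to-scan variation.

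At stake is how Aim 1 is read. Successes at any session number may mix response with ordinary variation, yet the result would be published as the number of sessions needed and used to set the course in Experiment 2.

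**Working it through.** **Inputs.** Threshold 0.028, sensitivity 87.5%, target 12.5%, cohorts of 3 and 15 subjects (section 10.a.i). Mean change 0.1018, SD 0.09296 and assumed SD range 0.085 to 0.10 (section 10.b). SDs of 0.05 and 0.03 are my assumptions. I take the threshold and the SD to be on the same scale.

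**The plan's own figure first.** One-sided paired t-test, N = 10, alpha 0.05, mean 0.1018, SD 0.093: noncentrality = 0.1018/0.093 × √10 = 3.46 on 9 degrees of freedom, power 0.93833. This matches the table, as do the other eight cells. The plan states no pass rate at 0.028 without effect, so there is nothing to reproduce for that.

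**Pass rate with no effect.** With normal changes and mean zero, P(change ≥ 0.028) = 1 − Φ(0.028/SD).

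| SD | Source | 0.028/SD | Pass rate |
|---|---|---|---|
| 0.10 | section 10.b, upper | 0.280 | 39.0% |
| 0.093 | section 10.b, middle | 0.301 | 38.2% |
| 0.085 | section 10.b, lower | 0.329 | 37.1% |
| 0.05 | assumed | 0.560 | 28.8% |
| 0.03 | assumed | 0.933 | 17.5% |
| 0.0243 | solved for 12.5% | 1.150 | 12.5% |

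**Pass rate with an effect, SD 0.093.** At the full quoted mean: 1 − Φ((0.028 − 0.1018)/0.093) = 78.6%. At half of it (0.0509): 59.7%. The corresponding rate with no effect is 38.2%.

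**A cohort of three with no effect, SD 0.093 (p = 0.382).**
- At least one success: 1 − 0.618³ = 76%.
- At least two: 3 × 0.382² × 0.618 + 0.382³ = 33%.
- All three: 0.382³ = 5.6%.

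**Dependence on the target.** I looked at an illustrative CRM simulation: one-parameter model, Gamma(1, 1) prior, five cohorts of three, start at 3 sessions, the same pass rate of 29%, 38% or 39% at every level, and 1,000 runs per setting. The plan gives no initial dose-response curve, so three were assumed. The early-stopping rule in section 4.d was not modelled.
- Target 12.5%: the run ended at the lowest level in 82% to 99.5% of runs.
- Target 87.5%: it ended at the highest level in every run.

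In both cases a session number was named although stimulation did nothing. Which number it was depended on the target.

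**The case against.** Several objections have force.

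- **The SD is a proxy.** It comes from the retrosplenial region in stimulated subjects, so it is from another region and may include variation in response. A reader might infer that 29-39% is the false-positive rate of Experiment 1. The documents do not support that: 0.05 is an assumption and not a floor, and smaller SDs give lower rates. The zero mean is also an assumption. Section 4.d.iii picks the target for its high baseline connectivity; if FC is measured there, regression to the mean could lower the rate.
- **The consequence depends on the target.** A reader might infer that Experiment 1 favours too few sessions whatever the target. The simulation contradicts this. With a high target, a background rate near 38% would rarely look like success, since three of three occurs 5.6% of the time.
- **Aim 1 does not say equivalent.** A reader might infer that 0.028 fails the aim because it is about 28% of the quoted mean (0.028/0.1018 = 0.275). Aim 1 asks for a substantial change; equivalence appears only in section 1.c, and the quoted mean is retrosplenial.
- **Background was not ignored.** An ROC cut-point implies a comparison condition, and section 4.d.iii reports no significant connectivity effect of off-target stimulation in the source study. Without the specificity, neither fact bounds the rate at 0.028.
- **Experiment 2 has the control.** It has a vertex arm, and its primary hypothesis is against vertex. But the FC test written for Specific Aim 2 is a pre-post paired test with no stated vertex comparison, so the background rate would not emerge from the plan as written.

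A single-arm dose-finding stage before a controlled experiment is a legitimate choice, and Experiment 1 is finished. A new arm is not called for.

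**Conclusion.** The point holds as a limit on what Experiment 1 can show. Without a vertex or zero-session reference, and with the specificity unreported, its session number cannot be attributed to stimulation rather than scan-to-scan change. That conclusion does not need any particular percentage.

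The size is conditional on normality, zero mean change and the SD: 37-39% with the section 10.b range as proxy, and less if the true SD without effect is smaller. Under these assumptions the rate stays above the written 12.5% target unless that SD is about 0.024 or less. The documents do not show which SD applies. They also do not show that the selected number is wrong, or in which direction it would err. The definition of the CRM target must be reconciled separately before that can be judged.

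**What to change.** 1. In section 10.a.i, report the specificity at 0.028 from the source data beside the 87.5% sensitivity.
2. In the Aim 1 analysis, apply the 0.028 threshold to the pre-post FC changes of the Experiment 2 vertex group, with the same scan processing and the same way of locating the parietal region. Report that background rate and the mean change with exact 95% intervals.
3. Show beside them the Experiment 1 success rate and mean change, by session number and pooled, also with intervals.
4. Describe the Experiment 1 result as the session number the algorithm selected, not controlled for scan-to-scan change, and not as the number required.
5. Label the comparison descriptive. Exceeding the background would not show that fewer sessions are insufficient, and the numbers are small: 3 of 3 against 6 of 16 gives a one-sided Fisher p of C(16,6)/C(19,9) = 8008/92378 = 0.087.

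The cost is analysis and wording only, since the vertex scans are already planned. The price is a more cautious Aim 1 conclusion. The reference is not concurrent with Experiment 1, and it is imprecise: 6 of 16, for example, has an exact 95% interval of about 15-65%.

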- 8) the Georgia Complex Figures task (for visual memory) – Participants are asked to copy a complex drawing, and reproduce it from memory after a 20-minute delay. The number of successful elements of the complex figure are recorded (~ 5 minutes without delay).
- 9) the Category Fluency test (for category fluency) – Participants are given a category (e.g. animals, tools) and are asked to name as many category members in 60 seconds as possible (~ 2 minutes).
- 10) a verbal paired associates test (for verbal memory) – This test is similar to the AMT, but instead of new items used at each time point, the same pairs are retested at the end of the week of stimulation (~ 5 minutes).
- 11) the Everyday Memory Questionnaire (EMQ) (a subjective memory assessment) – Participants are asked 13 questions to assess their impression of their memory function. For each question, participants rate how often a particular memory problem has occurred, e.g. not being able to recall a word, having to check something that has already been done (~ 3 minutes).
- 12) Neuro-QOL forms: Depression, Fatigue, Sleep Disturbance, Cognition-General, Cognition-Executive (a subjective mental health assessment) – Participants report outcome measures through computer adaptive tests (CAT), short forms, or scales. (~ 20 minutes).

v. Amsterdam Resting-State Questionnaire

The ARSQ will be administered immediately after each resting-state scan and includes 50 questions related to patterns of mentation that could occur during resting-state scanning (see Appendix F). For each question, the participant is asked whether they agree or disagree with a statement related to their thoughts in the scanner. This questionnaire generally takes < 8 minutes to complete.

vii. Experiment 1 (Completed)

[figure not shown]
Experiment 1 will study only healthy volunteers. During the first day of experimentation, all participants will have an initial scanning session where anatomical, resting-state, and DTI images will be collected. This will be followed by 1-5 days of rTMS (20-minutes per day). Participants may schedule the first MRI session, and the first session of rTMS anytime within two days. On the day after the last rTMS session (within 12-36 hours), a final anatomical and resting-state-scan will be collected. Immediately following each

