To reduce the risks of hearing loss associated with rTMS, all subjects will be fitted with hearing protection.

8. Subject Safety Monitoring

For healthy subjects, a credentialed physician or nurse practitioner will be on site for all rTMS administration and immediately available. This is the standard of care in community and academic clinical and experimental rTMS centers, nationwide. Study staff will be trained in rTMS administration, rTMS safety, and the measurement of the motor evoked potential threshold and will have performed 10 measurements under supervision. Study staff will monitor individuals during participation and participants will be encouraged to tell experimenters of any discomfort. Any subject exhibiting distress or who wishes to stop the experiment for any reason will be allowed to stop. Participants may withdraw at any time. Data of those participants that have completed at least the first session of either Experiment 1-2 (i.e. both MRI scan and behavioral assessment) will be kept and analyzed. A researcher may end experimentation for the following reasons:

- 1) Abnormal response to rTMS including the occurrence of a seizure, loss of consciousness, or excessive pain or headache produced by rTMS.
- 2) Withdrawal of consent and/or decision to terminate.
- 3) Excessive frustration exhibited by participants on behavioral tasks.
- 4) Decision by legal proxy or patient guardian to terminate participation.
- 5) Subjects withdrawn due to high motor thresholds above the maximum capacity of the stimulator
- 6) Subjects withdrawn due to discomfort of TMS

9. Outcome Measures

a. Primary outcome measures

- Pre-to-post rTMS difference in FC between the left parietal cortex and the left hippocampus (Experiments 1-2) in healthy subjects (Experiments 1 and 2).
- Pre-to-post rTMS difference in AMT scores in healthy subjects (Experiment 2).

b. Secondary outcome measures

- Pre-to-post rTMS difference in WPT-I scores after rTMS in healthy subjects (Experiment 2).

c. Exploratory outcome measures

- Correlations between memory performance and white matter integrity (Experiment 2).

10. Statistical Analysis

a. Analysis of data/study outcomes

i. Experiment 1

Specific Aim 1: To determine the number of rTMS sessions required to produce a substantial change in FC between the parietal cortex and hippocampus in healthy subjects.

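### Experiment 1's dose-finding rule counts FC responses as the event but targets the non-response rate (12.5%), so as written it searches for too few sessions

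*Combined protocol and SAP*

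**What the plan says.** Section 10.a.i keeps the CRM's toxicity vocabulary but translates it: "the term toxicity will correspond to efficacy of the rTMS". The event follows: "DLT will be defined as the FC change from baseline to post-stimulation ≥ 0.028". For the reference study the plan reports: "The sensitivity for the dichotomized FC change (at 0.028) in the parietal stimulation group was 87.50" percent. The target is then fixed: "TTL is set to 12.5%, which is equal to (1-sensitivity"). The dose sought is "the number of rTMS sessions that has a risk of DLT equal to the chosen TTL value of 12.5" percent.

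The purpose is stated twice. Aim 1 is to find "the number of rTMS sessions required to produce a substantial change in FC between the parietal cortex and hippocampus". Section 1.c says that "the MTD corresponds to the minimum number of sessions expected to produce the criterion change in FC".

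The remaining design features in Sections 4.d.vii and 10.a.i are levels of 1 to 5 sessions, five cohorts of 3, a start at 3 sessions, a one-parameter hyperbolic-tangent model and a Gamma(1,1) prior. If the result is not clear after 15 participants, Experiment 2 defaults to 5 sessions. Section 4.d.viii and the closing line of the Experiment 1 analysis carry the chosen number into Experiment 2.

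**The concern.** In a toxicity trial a low target makes sense because the event is harm. Here the event has been redefined as success, but the target was left at a low, harm-style value. A 12.5% target fits only if the event is failure to reach 0.028, with a curve that falls as sessions increase. The plan states neither.

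Experiment 1 exists to produce one number, and the target is the threshold that decides it. Followed literally, the rule looks for the session count at which about one person in eight responds, not the fewest sessions that reproduce the reference effect. Too low a count would under-dose Experiment 2 and could cost power. It would not bias parietal against vertex, because both groups receive the same number of sessions.

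**Working it through.** **1. The plan's own figure.** 1 − sensitivity = 1 − 0.875 = 0.125. The arithmetic is right, but 0.125 is the rate of the complement of the defined event.

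**2. Event and target side by side.**

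| Version | Event | Reference rate of event | Target | Consistent? |
|---|---|---|---|---|
| As written | change ≥ 0.028 | 87.5% | 12.5% | No |
| A | change ≥ 0.028 | 87.5% | 87.5% | Yes |
| B | change < 0.028, falling curve | 12.5% | 12.5% | Yes |

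**3. Decision after the first cohort (3 people at 3 sessions).** The plan gives no skeleton (prior response probabilities by level), so the skeletons here are assumptions. Model: p_i = s_i^a with a ~ Gamma(1,1). The next level is the one whose posterior mean p_i is closest to the target. With b_i = −ln s_i and one responder in three, the posterior mean has a closed form:

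p̂_i = [1/(1+b₃+b_i) − 2/(1+2b₃+b_i) + 1/(1+3b₃+b_i)] ÷ [1/(1+b₃) − 2/(1+2b₃) + 1/(1+3b₃)]

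Take the skeleton (.03, .07, .125, .20, .30), so b₃ = 2.079 and b₁ = 3.507:

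- Denominator: 0.3247 − 0.3877 + 0.1382 = 0.0752.
- Numerator for 1 session: 0.1518 − 0.2308 + 0.0931 = 0.0141.
- p̂₁ = 0.0141/0.0752 ≈ 0.188. Every higher level is further above 0.125, so the rule goes to 1 session.

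The same calculation for every outcome, with three skeletons per target: (.03,.07,.125,.20,.30), (.05,.125,.20,.30,.40) and (.02,.04,.08,.125,.20) for 12.5%; (.60,.75,.875,.92,.95), (.50,.65,.78,.875,.93) and (.40,.55,.70,.80,.875) for 87.5%. Version B uses the low skeletons with the level order reversed.

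| Responders of 3 | As written | Version A | Version B |
|---|---|---|---|
| 0 | 3–4 sessions | 5 | 5 |
| 1 | 1 | 5 | 5 |
| 2 | 1 | 4–5 | 5 |
| 3 | 1 | 3 | 2–3 |

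With one or two responders, the written rule moves in the opposite direction to both consistent versions.

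**4. Full design simulated to 15 participants** (assumed true response at 1 to 5 sessions; the early-stopping rule in Section 4.d.vii was not simulated).

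- Response 50/60/70/80/87.5%: the written target selects 1 session in about 100% of trials, where true response is 50%.
- Response 20/35/55/75/87.5%: 1 session in 92–97%, where true response is 20%.
- On these two curves an 87.5% target selects levels with mean true response of 82–86%.
- A separate set used four other skeletons, five curves, moves capped at 2 sessions, and the posterior mean of a plugged into the curve. The written target ended at 1 or 2 sessions in 81–100% of runs, and an 87.5% target at 4 or 5 in 86–100%.

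**5. Scale of the target.** Section 10.b gives a retrosplenial mean change of 0.1018 and SDs of 0.085 to 0.10. Under a normal model, P(change ≥ 0.028) is 0.807 at SD 0.085 and 0.770 at SD 0.10. With a mean change of zero it is 0.371 to 0.390. On those SDs, which need not apply to the hippocampal pair, noise alone would exceed a 12.5% target. Under a flat 38% response neither target detects the absence of effect: the written one picks 1 session in 95–96% of trials and the 87.5% one picks 5 in over 99%. That case is therefore not evidence for either.

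**The case against.** **This may be only careless wording.** Section 4.d.vii expects sessions to drop by 1 or 2 after a large increase and to rise by 0 to 2 after little or none. The written target does this at the extremes: 3 of 3 gives 1 session, and 0 of 3 gives 3–4. Version A stays at 3 after 3 of 3, while version B can drop. So the team may have run a coherent non-response coding and described it badly. That is possible, but nothing in the documents says so, and one or two responders in three still send the written rule down.

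**Experiment 1 is finished and no harm is shown.** This is correct. Coding, skeleton, cohort results and the selected number are all absent, and the 5-session default may have been used. But the default applies only when the result is not clear, a term the plan does not define. A stable recommendation of 1 session would look clear.

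**The sizes depend on assumptions.** This stands. Both curves listed first in step 4 already exceed 12.5% at 1 session. With a steep curve (2/5/12.5/60/87.5%), 1 session is chosen in only 7–33% of trials and 3 sessions in 24–54%. Even so, the rule settles mostly on levels with true response of about 12.5% or less. With the plug-in estimate, 0 of 3 gives 4–5 sessions on the low skeletons of step 3. On one of the other skeletons 1 of 3 gives 2 sessions rather than 1.

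**An 87.5% target has its own weakness.** It comes from a five-session study and pulls towards the top level. If response were truly 87.5% at every level, it would pick 1 session in only 11–15% of trials. This matters for choosing the remedy but does not rescue the written target.

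**Conclusion.** The concern holds: the Experiment 1 decision threshold is wrong as written. That conclusion needs only the text of Section 10.a.i and rests on no assumed model. The direction of the error, towards fewer sessions, held across the assumed skeletons whenever one or two of the first three participants responded. How often exactly 1 session is chosen depends on the skeleton, the estimator and the true curve.

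The consequence for the trial as run is unknown. The point must be fixed because the threshold that decides Aim 1 is wrong in the plan, not because damage to Experiment 2 has been shown.

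**What to change.** Make event and target describe the same outcome. Either keep the event as change ≥ 0.028 with a target of 87.5%, or define it as change < 0.028 with a target of 12.5% and a curve that decreases in sessions. This costs two lines of wording.

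Because Experiment 1 is complete, also report the coding, skeleton and target actually used, the responders at each session level, and the number selected. If a consistent version was run, the wording correction is enough.

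If the rule was run as written, do not describe the selected number as optimal or required. Restate the basis for Experiment 2's session count, for example by invoking the plan's own 5-session default. A refit with the matched target is cheap but is only a sensitivity analysis. With response rising from 50% to 87.5%, about 12 of the 15 participants would have been treated at 1 session, 3 at 3 sessions, and almost none at 4 or 5. The refit then depends on the skeleton: 5 sessions in 96–99% of trials with the low skeletons, but 5 in 11–58%, 4 in 31–65% and 3 in 9–39% with the high ones. No new participants are needed, but the Experiment 1 conclusion may have to be softened.
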